10.1 ASAS20, ASAS40, ASAS 5/6 response and ASAS partial remission

The ASAS20 is defined as an improvement of at least 20% and absolute improvement of at least 1 unit on a 0 to 10 numeric rating scale (NRS) in at least 3 of the 4 following domains:

- PGADA (see [Section 10.7](#))
- Pain assessment (the total spinal pain NRS score; [Section 10.8](#))
- Function (represented by BASFI, [Section 10.4](#))
- Inflammation (the mean of the BASDAI Questions 5 and 6, concerning [REDACTED]
[REDACTED])
- and absence of deterioration in the potential remaining domain (deterioration is defined as a relative worsening of at least 20% and an absolute worsening of at least 1 unit).

The ASAS criteria for 40% improvement are defined as relative improvements of at least 40%, and absolute improvement of at least 2 units on a 0 to 10 NRS in at least 3 of the 4 domains and no worsening at all in the remaining domain.

The ASAS 5/6 response is defined as at least 20% improvement in 5 of 6 domains, including spinal mobility (lateral spinal flexion) and CRP as more objective measures (Brandt et al, 2004).

The ASAS partial remission response is defined as a score of ≤ 2 units on a 0 to 10 unit scale in all 4 domains listed above for ASAS20.

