8 EFFICACY ANALYSES

Missing efficacy data will be imputed as described in [Section 4.2.1](#) prior to reporting. As a sensitivity analysis, summaries will be repeated based on non-imputed (OC) data for the following variables:

- ASAS40 response relative to AS0008 Baseline at each visit in AS0009.
- ASAS20 response relative to AS0008 Baseline at each visit in AS0009.
- ASAS 5/6 response relative to AS0008 Baseline at each visit in AS0009.
- Change from AS0008 Baseline in BASDAI at each visit in AS0009.

A further sensitivity analysis will be performed for ASAS40 and ASAS20 response relative to AS0008 Baseline. The response endpoint will be re-derived and summarized based on the mean value (across multiple imputations) of the individual component scores after imputation for missing data.

Efficacy variables will be summarized and listed for the FAS. Summaries of MASES will be restricted to subjects with a MASES >0 at AS0008 Baseline. Maintenance of response summaries will be restricted to subjects who achieved a response at AS0008 Week 12 for the specific endpoint (where the response at AS0008 Week 12 is taken directly from the AS0008 datasets).

Responder variables (e.g. ASAS40 response) will be derived relative to the AS0008 Baseline and summarized using n and percentage at each visit, by treatment group at completion of AS0008 and overall.

Maintenance of response will be assessed for ASAS40, ASAS20 and ASAS5/6. The responses will be derived relative to AS0008 Baseline and summarized using n and percentage at each post-AS0008 Baseline visit, by treatment sequence across AS0008 and AS0009. These summaries will therefore include AS0008 Week 1, 2, 4, 8 12, 16, 24, and 36 and AS0009 EV (AS0008 Week 48), Week 12, 24, 36, 48, 60, 72, 84, 96, 108, 120, 132, 144, 156, 168, 180, 192, 204, and Week 208. AS0008 Week 1 and 2 are not applicable for ASAS5/6 response.

Absolute and change from AS0008 Baseline for all continuous efficacy variables will be summarized descriptively by visit, by treatment group at completion of AS0008 and overall.

Any data collected at the SFU visit will be excluded from all efficacy summaries; this data will be included in the listings only.

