8.1.1 Assessment in Axial Spondyloarthritis International Society Response Criteria

The ASAS20 response is defined as an improvement (decrease) of at least 20% and absolute improvement of at least 1 unit on a 0 to 10 numeric rating scale (NRS) in at least 3 of the 4 following domains (Anderson, 2001):

- PGADA
- Pain assessment (total spinal pain, question 1 from total and nocturnal spinal pain questionnaire)
- Function (represented by the BASFI)
- Inflammation (the mean of the BASDAI questions 5 and 6, concerning morning stiffness, intensity and duration)

This must be accompanied by the absence of deterioration in the potential remaining domain. Deterioration is defined as a relative worsening of at least 20% and an absolute worsening of at least 1 unit.

The ASAS criteria for 40% improvement are defined as relative improvement of at least 40% and absolute improvement of at least 2 units on a 0 to 10 NRS in at least 3 of the 4 domains and no worsening at all in the remaining domain (where worsening is defined as any worsening at all relative to baseline).

The comparison of changes to the specified cut-offs (i.e., ≥ 1 or ≥ 2 units) will be based on non-rounded data.

The ASAS 5/6 response is defined as at least 20% improvement in 5 of 6 domains, which includes, in addition to the 4 domains above, spinal mobility (lateral spinal flexion as recorded for BASMI) and CRP as more objective measures (Brandt et al, 2004). In the calculation of the ASAS 5/6 response the actual assessment value for the lateral spinal flexion will be used and not the transformed value used in the calculation of the BASMI score.

If the CRP value is below the lower limit of quantification (LLOQ) defined in AS0008 then it will be set to half of the LLOQ (as described in [Section 8.1.12](#)).

The ASAS partial remission (ASAS-PR) response is defined as a score of ≤ 2 units on a 0 to 10 unit scale in all 4 domains listed above.

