8.1.1.1 Data Handling Rules for ASAS40 and ASAS20

The ASAS40 and ASAS20 will be derived based on the data handling rules below. These rules will be implemented prior to performing any NRI or MI procedures, and will therefore be integrated as part of any OC summaries i.e., they are considered as OC data.

The rules will apply for all visits in AS0009 where at least one component is present at the specific visit. For summaries of maintenance of response, the ASAS responses at visits in AS0008 will not be re-derived and will be taken directly from the AS0008 database.

- If 3 components are present (and the other component is missing), and all 3 components meet the criteria for improvement, the remaining component will be assumed not to have deteriorated and the subject will be considered a responder for ASAS40 (or ASAS20).
- If at least 1 component is present (and 1 or more other components are missing) and meets the criteria for a deterioration, the subject is a non-responder for ASAS40 (or ASAS20)
- If a single component value is missing at Baseline (and the other 3 components are not missing), the percent and absolute improvement from Baseline for all visits for that component will be set to 0 for purposes of ASAS response calculations. Thus, the subject may still be considered a responder for ASAS40 (or ASAS20) if the other 3 components all meet the criteria for improvement.
 - Note that for MI any component with a missing Baseline will be excluded from the MI modelling as Baseline is included as a covariate in the model.
 - Thus, for the MI this will mean that a maximum of 3 components only will be available at each visit and all 3 components must therefore demonstrate an improvement based on the imputed values in order for the subject to be defined as a responder at that visit. In all other cases the subject will be regarded as a non-responder when the response is re-derived based on the imputed components.
- If more than 1 component value is missing at Baseline, the percent and absolute improvement from Baseline for all visits for those components will be set to 0 for purposes of ASAS response calculations. Thus, the subject would be considered a non-responder for ASAS40 (and ASAS20) at all visits.
 - Any subject with more than 1 component missing at Baseline will therefore be excluded from any summaries based on MI as there would be insufficient data available to derive a response.

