- If the Baseline value for a given component is 0 the percent improvement from Baseline is not calculable. In this case the following rules will apply:
 - If the post-Baseline value is also 0, the percent and absolute improvement at that visit will be treated as 0 for purposes of ASAS response calculations.
 - If the post-Baseline value is greater than 0 and the arithmetic change from Baseline is ≥ 1.0 , then that component will be treated as having a 20% worsening and a 1-unit absolute worsening from Baseline for purposes of ASAS response calculations (i.e., the component has deteriorated).
 - If the post-Baseline value is greater than 0 and the arithmetic change from Baseline is < 1.0 , then that component will be treated as having neither improved nor worsened for purposes of ASAS response calculations.

- If the post-Baseline value is missing, it will be regarded as 0 and the percent and absolute improvement at that visit will be treated as 0 for purposes of ASAS response calculations (NB: For the MI procedure the observed data will be included in the model as received without imputation with 0, and the percent and absolute improvement will be assumed to be 0 after performing the MI, regardless of the imputed absolute values)
- For component scores with a Baseline value >0 and a post-Baseline value of 0, percentage improvement will be calculated as for any other non-missing data.

With regards to the BASFI component see [Section 8.1.3](#) for calculation in case of missing values of single questionnaire items.

With regards to the BASDAI component see [Section 8.1.4](#) for calculation in case of missing values of single questionnaire items.

Further details regarding the assumptions and assignment of worst-case imputations for NRI are provided in [Section 12.1](#).

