12 APPENDICES

12.1 Data Handling Rules for ASAS20, ASAS40 and ASAS5/6 Response

The rules for handling missing data in relation to defining the achievement of ASAS20 and ASAS40 responses are provided in [Table 12-1](#). This table also indicates, where appropriate, the imputation as a non-responder (DTYPE = WC) in the analysis datasets for the NRI analyses. For tables presented on OC data, the data selected will include all instances where DTTYPE is not populated in the analysis datasets.

Table 12-1: Data Handling Rules for ASAS20 and ASAS40

Components	Component Status	ASAS ^a	DTYPE
4 components present	3 or more components improved ≥40% and ≥2 units AND no deterioration in remaining component	Y	
4 components present	3 components improved ≥40% and ≥2 units AND remaining component deteriorated ≥20% and ≥1 unit	N	
At least 1 component present	1 or more component(s) has deteriorated ≥20% and ≥1 unit	N	
3 components present	3 or more components improved ≥40% and ≥2 units	Y	
3 components present	2 components improved ≥40% and ≥2 units AND no deterioration in remaining component(s)	N	WC
3 components present	1 or 0 components improved ≥40% and ≥2 units AND no deterioration in remaining component(s)	N	
2 components present	2 or 1 components improved AND no deterioration in remaining component(s)	N	WC
2 components present	0 components improved	N	
1 or 0 components present	1 or 0 components improved ≥40% and ≥2 units AND no deterioration in remaining component(s)	N	WC

^a Rules are based on ASAS40, similar rules will be implemented for ASAS20 response where improvement is defined as a change ≥20% and ≥1 units.

WC = worst case.

Similar rules for defining the achievement of ASAS5/6 response are presented in [Table 12-2](#).

Table 12-2: Data Handling Rules for ASAS5/6 Response

Components	Component Status	ASAS	DTYPE
6 components present	5 or more components improved $\geq 20\%$	Y	
6 components present	4 or fewer components improved $\geq 20\%$	N	
5 components present	5 components improved $\geq 20\%$	Y	
5 components present	4 components improved $\geq 20\%$	N	WC
5 components present	3 or fewer components improved $\geq 20\%$	N	
4 components present	4 or 3 components improved $\geq 20\%$	N	WC
4 components present	2 or fewer components improved $\geq 20\%$	N	
3 components present	3 or 2 components improved $\geq 20\%$	N	WC
3 components present	1 or 0 component(s) improved $\geq 20\%$	N	
2 components present	2 or 1 components improved $\geq 20\%$	N	WC

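### SAP Table 12-1 gives ASAS40 the ASAS20 deterioration threshold; coded as written, it could overstate ASAS40 at Week 48

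*SAP*

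**What the plan says.** **Definition.** For ASAS40, Protocol 10.1 asks for a 40% and 2-unit improvement "in at least 3 of the 4 domains and no worsening at all in the remaining domain". SAP 8.1.1 repeats this and spells it out: "no worsening at all in the remaining domain (where worsening is defined as any worsening at all relative to baseline". The looser criterion appears only in the ASAS20 definition of SAP 8.1.1: "Deterioration is defined as a relative worsening of at least 20% and an absolute worsening of at least 1 unit".

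**Table 12-1 (SAP 12.1).** The table uses the ASAS40 improvement cut-offs. With four components present, row 1 gives Y if three or more improved and the remaining one shows no *deterioration*. Row 2 gives N where "3 components improved ≥40% and ≥2 units AND remaining component deteriorated ≥20% and ≥1 unit". A further row gives N on the same threshold whenever at least one component is present. Footnote a reads: "Rules are based on ASAS40, similar rules will be implemented for ASAS20 response where improvement is defined as a change ≥20% and ≥1 units". So only the improvement cut-off changes between the two endpoints.

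**SAP 8.1.1.1.** One rule serves both endpoints: a component that "meets the criteria for a deterioration, the subject is a non-responder for ASAS40 (or ASAS20"). If the baseline is zero and the rise is below 1.0, "then that component will be treated as having neither improved nor worsened for purposes of ASAS response calculations".

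**Multiple imputation (separate points).** SAP Section 8 says that the ASAS40/ASAS20 sensitivity endpoint is "re-derived and summarized based on the mean value (across multiple imputations) of the individual component scores after imputation". SAP 4.2.1 instead derives response within each imputation and averages the percentages. Table 4-2 footnote b averages ASDAS-CRP within each subject before summarizing, whereas Step 3 of 4.2.1 combines the imputed datasets by Rubin's rules.

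**The concern.** The governing definition of ASAS40 and the table that assigns responder status do not agree. SAP 8.1.1 defines *deterioration* only by the ASAS20 threshold. Row 1 read with that definition makes a responder of a subject with three improved domains and a small worsening in the fourth. Read with the ASAS40 rule of 8.1.1, the same subject falls in no row at all. SAP 3.10, which lists the departures from the protocol, mentions no change to ASAS40, so this does not look intended.

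ASAS40 at Week 48 is a secondary efficacy variable, analyzed mainly by NRI. The same derivation feeds the other AS0009 visits, the subgroup summaries, the AS0009 part of maintenance of response and the ADAb figures. SAP 3.1 rounds to 12 decimals to stop threshold errors from changing responder status; a wrong threshold is a larger risk of the same kind.

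**Working it through.** The plan states no ASAS40 rate or component distribution, so there is no figure to reproduce.

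**1. The two rules.** Let b be baseline, v the later value and w = v − b for the one domain that did not improve.
- Text (Protocol 10.1, SAP 8.1.1): non-responder if w > 0.
- Table 12-1: non-responder if w ≥ 1 and w/b ≥ 0.20. From b = 0, SAP 8.1.1.1 uses w ≥ 1.
- Conflict: w > 0 with w < 1 or w/b < 0.20.

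**2. Worked cases.** Three domains go 7→3 (4 units, 4/7 = 57%, improved). The fourth varies:

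| Fourth domain | w/b | Text | Table 12-1 |
|---|---|---|---|
| 5→5 | 0 | Y | Y |
| 5→5.5 | 10% | N | Y |
| 6→7 | 16.7% | N | Y |
| 8→9.5 | 18.8% | N | Y |
| 0→0.5 | not calculable | N | Y |
| 5→6 | 20% | N | N |
| 0→1 | not calculable | N | N |

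**3. Direction.** Every worsening that fails under the table also fails under the text, so the table can only add responders. In 200,000 random four-component profiles, 1,617 were responders by the table only and 0 by the text only.

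**4. Which components conflict.** Counting all worsening pairs on a 0–10 scale (step sizes assumed; these are counts, not frequencies):
- Steps of 1 (PGADA, pain): 11×10/2 = 55 pairs. Only a 1-point rise from 6, 7, 8 or 9 conflicts, so 4/55.
- Steps of 0.5 (inflammation): 21×20/2 = 210 pairs. Rises of 0.5, 1.0 and 1.5 give 20 + 8 + 2 = 30 conflicts.
- Steps of 0.1 (BASFI): 101×100/2 = 5,050 pairs. Rises of 0.1–0.9 give 864 and rises of 1.0–1.6 give 154, together 1,018.

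BASFI is therefore the most exposed.

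**5. Observed-case data.** Take three components present, two improved and the third slightly worse. Under 8.1.1 this subject cannot be an ASAS40 responder whatever the missing component is. Table 12-1 flags the subject as a worst-case imputation, which removes a certain non-responder from the observed-case data.

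**6. Size, on assumed inputs.** Simulated ASAS40 percentage under Table 12-1 minus that under 8.1.1, all four components observed. Subjects = points × 285/100.

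| Scenario grid | Points | Subjects of 285 |
|---|---|---|
| A: components alike (baseline mean 5.5–7.0, Week 48 mean 2.5–4.5, r 0.4–0.75; 480 scenarios) | 0.02 to 1.6, median 0.4 | 0.1 to 4.6, median 1.1 |
| B: BASFI lags (its baseline 4.5–5.5, mean gain 1.5–2.5, r 0.4–0.6 with the other components; 1,296 scenarios) | 0.2 to 5.8, median 2.0; central 90% of scenarios 0.6 to 4.6 | 0.6 to 16.5, median 5.7; central 90% 1.7 to 13.1 |

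In B, about 98% of the conflicting worsenings are in BASFI. The zero-baseline rule alone contributes at most 0.4 points (0.4 × 2.85 = 1.1 subjects).

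**7. Section 8 against 4.2.1.** Response is a threshold function, so response at the mean of the imputations is not the mean of the responses. With 100 imputations, an assumed on-treatment mean of 3.0–4.5, SD 2.3 and 10% missing, the Section 8 wording shifts ASAS40 by −1.9 to +2.7 points and ASAS20 by +0.2 to +2.8. NRI is unaffected.

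**8. Footnote b against Step 3.** The mean is the same either way, because only the order of averaging changes. Averaging within subject removes between-imputation spread. With 100 imputations, n = 142 and predictor R² 0.3–0.5 (assumed), the SD is 0.96–0.97 and the SE 0.93–0.95 of the Step 3 values at 10% missing. At 30% missing the ratios are 0.89–0.92 and 0.77–0.83. Order statistics change too.

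**The case against.** The best defence is that SAP 8.1.1 states the correct rule explicitly and a programmer would follow it. Section 12.1 is introduced as missing-data handling. Table 12-1 is also incomplete: four components present, fewer than three improved and none deteriorated matches no row, so 8.1.1 has to be consulted anyway. Rows that assign N are sufficient conditions and do not contradict 8.1.1 by themselves; overstatement needs row 1 to borrow the ASAS20 meaning of *deterioration*. This is why the conclusion is *could* and not *will*. It does not remove the conflict: rows 1 and 2 concern complete data, the table sets responder status in the analysis datasets, and footnote a ties it to ASAS40.

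Several limits on reach stand. SAP 4.2.1 sends the MI derivation to 8.1.1.1 and not to Table 12-1, so MI is touched through the shared wording there and most clearly through the zero-baseline rule. SAP 3.1 bases percentages on the analysis set with a Missing row, so the flag in step 5 moves a subject to Missing and need not change the observed-case responder percentage. AS0008 responses, including the Week 12 selection for maintenance of response, are not re-derived.

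On size, the scenario ranges are not uncertainty intervals, grid B is built so that BASFI lags, 285 is an enrolment ceiling and not the FAS, and missing data under NRI would shrink the effect. All of that is fair. The two MI points do not bear on Table 12-1 and are reported only because they need the same edit.

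**Conclusion.** The concern holds. SAP Table 12-1 and the zero-baseline rule in 8.1.1.1 permit an ASAS40 responder whom Protocol 10.1 and SAP 8.1.1 exclude. That follows from the wording and needs no assumption, as does the direction: upwards only. The size cannot be computed from the documents. Each misclassified subject is worth 100/285 = 0.35 percentage points at the maximum enrolment, and a shift from a fraction of a point to a few points is plausible, depending mainly on how BASFI behaves.

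The consequence is limited. This is a single-arm descriptive extension with a primary safety objective and no hypothesis test, and the governing definition is right in both documents. It should still be fixed, because a reported secondary variable depends on which section was coded. The Section 8 conflict can move only the MI sensitivity estimate, in either direction for ASAS40. The footnote b conflict understates the spread of an *other* efficacy variable without moving its mean.

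**What to change.** - **Table 12-1:** for ASAS40, replace the ≥20% and ≥1 unit criterion with any worsening relative to AS0008 Baseline, in the responder and the non-responder rows. Give ASAS20 its own rows with ≥20% and ≥1 unit.
- **SAP 8.1.1.1:** state the worsening criterion separately for ASAS40 and ASAS20, and count any increase from a zero baseline as worsening for ASAS40.
- **SAP Section 8:** replace the averaged-components sentence with the 4.2.1 rule.
- **Table 4-2 footnote b:** delete the within-subject averaging and apply Step 3.
- **Programs:** confirm which ASAS40 rule was coded.

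The cost is wording, table rows and one code check. If the table's rule was programmed, the ASAS40 outputs need rerunning and the percentages may fall slightly. The ASDAS-CRP SD and SE may widen slightly.

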12.2 Classification of the SF-36 questionnaire

Table 12-3 describes the 8 different scores calculated from the SF-36 questionnaire.

Table 12–3: Classification of the SF-36 questionnaire

Scales
Physical Functioning
Role-Physical
Bodily Pain
General Health
Vitality
Social Functioning
Role-Emotional
Mental Health

This

12.3 Identification of Opportunistic infections

Opportunistic infections are identified in two steps:

Step 1: Refer to column B of the spreadsheet (Opportunistic infections MedDRA v 19.xlsx) which identifies the PTs to be classified as opportunistic infections using either a single “x” or a double “xx”.

- TEAEs which code to a PT flagged with a single “x” need to also be serious in order to be considered an opportunistic infection.
- All TEAEs which code to a PT flagged with a double “xx” are considered to be an opportunistic infection, regardless of seriousness.

All serious TEAEs in the study database which code to a PT flagged with a single “x” and all TEAEs in the study database which code to a PT flagged with a double “xx” will be summarized as an opportunistic infection in the stand-alone table.

Step 2: Refer to column C of the spreadsheet which identifies the PTs that need to be evaluated on a case-by-case basis by the study physician in order to determine whether it is a true opportunistic infection or not. The process for physician review is as follows:

1. Study programming team creates a spreadsheet which lists all of the subjects with a TEAE present in the database which codes to a PT identified as case-by-case. Information from the AE dataset to be included in the spreadsheet: Subject ID, AE verbatim term, SOC, High Level Term, Lower Level Term, PT, AE start date, AE end date, seriousness, severity, relationship to study medication, action taken. Additionally, a column will be included where the study physician can document their decision on the case.
2. Study physician reviews the cases in the spreadsheet and indicates in the additional column which AEs are confirmed to be opportunistic infections via a single “x”.
3. Study programming team incorporates these decisions into the AE dataset by merging the study physician decisions for individual subjects / PTs and flagging the confirmed opportunistic infections as such in the dataset.

All subjects enrolled with a case-by-case PT reported that has been confirmed by the study physician to be an opportunistic infection will be summarized as such in the stand-alone table, along with all of the events identified in Step 1 of this process.

[figure not shown]
The timing and frequency of Step 2 should be outlined and agreed to by the study team at the beginning of the study. It is suggested that this process be executed multiple times throughout the course of the study, more frequently in the weeks leading up to database lock, and one final time immediately prior to database lock.

Following the initial physician review of case-by-case events, subsequent reviews will be based on the cumulative set of case-by-case events present in the database at each time point of spreadsheet creation. Physician decisions from previous runs should be retained in each subsequent run. The final run of the spreadsheet, with all study physician decisions on the full set of case-by-case events, will be archived at the conclusion of the study.

